1.0 STUDY SUMMARY

Name of Sponsor: Takeda Development Center Americas, Inc. (TDC Americas) [name] [contact]	Compound: TAK-788
Study Identifier: TAK-788-1005 (CA24171)	Phase: 1
Protocol Title: A Phase 1, Randomized, 2-Period, 2-Sequence, Crossover Study to Evaluate the Effect of High-Fat Meal on TAK-788 Pharmacokinetics in Healthy Adult Subjects	
Study Design: This is an open-label, randomized, 2-period, and 2-sequence crossover high-fat meal effect study in healthy adult subjects. Subjects will undergo screening evaluations to determine eligibility within 21 days prior to dosing. In this study, subjects will be admitted to the clinical facility the day prior to dosing in each period (Day -1). Subjects will be randomized on Day 1 of Period 1 to a crossover sequence in a 1:1 ratio and administered a single oral dose of 160 mg TAK-788 on Day 1 with or without a high-fat meal of each period (ie, Period 1 and Period 2). Each dose will be separated by a washout period of 10 days. Blood samples for TAK-788 PK will be collected predose and up to 240 hours following each TAK-788 dose. Subjects will receive the following treatments on one occasion in a crossover fashion to evaluate the effect of a high-fat meal: 
• Treatment A (reference): 4 × 40 mg TAK-788 capsules, fasted conditions• Treatment B (test): 4 × 40 mg TAK-788 capsules with a high-fat meal* * 800-1000 total calories, 500-600 calories, 55-65 g, or 50% from fat (FDA FE 2019) Subjects will remain at the clinical site until the 240-hour study assessments in Period 2 are completed. All doses of TAK-788 will be administered at the clinic during this study. Spirometry as the pulmonary function test (PFT) may be performed in the event of a pulmonary adverse event (AE) and deemed clinically necessary, as determined by the Investigator or designee. A final safety follow-up phone call will occur 30 ± 2 days after the last TAK-788 dose to determine if any AEs have occurred since the last study visit. Replacement of discontinued or withdrawn subjects due to any reason will be assessed on a case by case basis by the Sponsor and PI to ensure a minimum of 12 PK-evaluable subjects complete the study.	
Study Primary Objective: 
• To characterize the effect of a high-fat meal on the PK of TAK-788 administered as a proposed commercial product. Study Secondary Objective: 
• To assess the PK of active metabolites AP32960 and AP32914 of TAK-788. Study Exploratory Safety Objective: 
• To collect the safety data of TAK-788 following a single oral dose in healthy adult subjects.	
Study Subject Population: Healthy male and female subjects aged 19 to 55 years inclusive, at screening. Body Mass Index (BMI) 18.5-30.0 kg/m ² , inclusive, at screening.	

Planned Number of Subjects: Fourteen healthy adult subjects will be enrolled, randomized, and dosed in the high-fat meal effect study.	Planned Number of Sites: 1
Dose Levels: Treatment A (reference): 4 x 40 mg TAK-788 capsules, fasted conditions Treatment B (test): 4 x 40 mg TAK-788 capsules with a high-fat meal All doses of TAK-788 will be orally administered at the clinic with 8 fluid oz (240 mL) of water.	Route of Administration: Oral
Duration of Treatment: Single oral dose of TAK-788 (4 x 40 mg) on Day 1 of each period. There will be a washout period of 10 days between the dose of TAK-788 in Period 1 and Period 2.	Planned Study Duration: Approximately 61 days \pm 2 days including screening period and follow-up.
Criteria for Inclusion: Subjects must fulfill the following inclusion criteria to be eligible for participation in the study: 
1. Healthy, adult, male or female, 19 - 55 years of age, inclusive, at screening.2. Continuous non-smoker who has not used nicotine-containing products for at least 20 years prior to the first dosing and throughout the study, based on subject self-reporting.3. Body mass index (BMI) ≥ 18.5 and $\leq 30.0 \text{ kg/m}^2$, at screening.4. Medically healthy with no clinically significant medical history, physical examination, laboratory profiles, vital signs, or electrocardiograms (ECGs), as deemed by the Investigator or designee. Has liver function tests (LFTs) including alanine aminotransferase (ALT), aspartate aminotransferase (AST), alkaline phosphatase (ALP), and total bilirubin less than or equal to the upper limit of normal at screening and at first check-in.5. For a female of nonchildbearing potential, must have undergone one of the following sterilization procedures at least 6 months prior to the first dosing:
• hysteroscopic sterilization;• bilateral tubal ligation or bilateral salpingectomy;• hysterectomy;• bilateral oophorectomy;or be postmenopausal with amenorrhea for at least 1 year prior to the first dosing and follicle stimulating hormone (FSH) serum levels consistent with postmenopausal status.6. Female subjects of childbearing potential will be advised to remain sexually inactive or to keep the same birth control method for at least 30 days following the last TAK-788 dosing as indicated in Appendix D.7. Female subjects must agree not to donate ova/oocytes during the study and for at least 30 days following the last TAK-788 dosing as indicated in Appendix D.8. A non-vasectomized male subject must agree to use a condom with spermicide or abstain from sexual intercourse during the study until 30 days after the last dosing. (No restrictions are required for a vasectomized male provided his vasectomy has been performed 4 months or more prior to the first dosing of study drug. A male who has been vasectomized less than 4 months prior to study first dosing must follow the same restrictions as a non-vasectomized male).9. Male subjects must agree not to donate sperm from the first dosing until 30 days after the last TAK-788 dosing.	

10. Understands the study procedures in the informed consent form (ICF) and be willing and able to comply with the protocol.

Criteria for Exclusion:

The subject must be excluded from participating in the study if the subject:

1. Is mentally or legally incapacitated or has significant emotional problems at the time of the screening visit or expected during the conduct of the study.
2. History or presence of clinically significant medical or psychiatric condition or disease in the opinion of the Investigator or designee.
3. History of any illness (including hyperlipidemia and diabetes since high fat meal is required) that, in the opinion of the Investigator or designee, might confound the results of the study or poses an additional risk to the subjects by their participation in the study.
4. History or presence of alcoholism or drug abuse within the past 2 years prior to the first dosing.
5. History or presence of hypersensitivity or idiosyncratic reaction to the study drugs or related compounds.
6. History or presence of any previous lung disease and/or current lung infection.
7. Female subjects with a positive pregnancy test or who are lactating.
8. Positive urine drug or alcohol results at screening or first check-in.
9. Positive results at screening for human immunodeficiency virus (HIV), hepatitis B surface antigen (HBsAg), or hepatitis C virus (HCV).
10. Positive test result for active COVID-19.
11. Seated blood pressure is less than 90/40 mmHg or greater than 140/90 mmHg at screening.
12. Seated heart rate is lower than 40 bpm or higher than 99 bpm at screening.
13. QTcF interval is >460 msec (males) or >470 msec (females) or ECG findings are deemed abnormal with clinical significance by the Investigator or designee at screening.
14. Creatinine clearance <90 mL/min at screening (calculated using the Cockcroft-Gault formula).
15. Unable to refrain from or anticipates the use of:
 - Any drug, including prescription and non-prescription medications, herbal remedies, or vitamin supplements within 14 days prior to the first dosing and throughout the study. Medication listed as part of acceptable birth control methods will be allowed (refer to [Appendix D](#)). Thyroid hormone replacement medication may be permitted if the subject has been on the same stable dose for the immediate 3 months prior to the first dosing. Acetaminophen (up to 2 g per 24 hour period) may be permitted during the study, only after initial dosing, if necessary, to treat AEs.
 - Any drugs known to be inhibitors or inducers of cytochrome P450 (CYP)3A enzymes and/or p-glycoprotein (P-gp), including St. John's Wort, within 28 days prior to the first dosing and throughout the study. Appropriate sources (eg, Flockhart TableTM) will be consulted to confirm lack of PK/pharmacodynamics interaction with study drugs.
16. Has been on a diet incompatible with the on-study diet, in the opinion of the Investigator or designee, within the 30 days prior to the first dosing and throughout the study.
17. Donation of blood or significant blood loss within 56 days prior to the first dosing.
18. Plasma donation within 7 days prior to the first dosing.
19. Participation in another clinical study within 30 days for a small molecular drug or 90 days for a biologic drug prior to the first dosing. The 30-day or 90-day window will be derived from the date of the last blood collection or dosing, whichever is later, in the previous study to Day 1 of Period 1 of the current study.

Main Criteria for Evaluation and Analyses:

Primary Endpoints

The following PK parameters will be analyzed for TAK-788.

- Time of first occurrence of C_{\max} (T_{\max}).
- Maximum observed concentration (C_{\max}).
- Area under the concentration-time curve from time 0 to infinity, calculated using the observed value of the last quantifiable concentration (AUC_{∞}).
- Area under the concentration-time curve from time 0 to the time of the last quantifiable concentration (AUC_{last}).

Secondary Endpoints

The following PK parameters will be analyzed for active metabolites (AP32960 and AP32914) of TAK-788.

- Time of first occurrence of C_{\max} (T_{\max}).
- Maximum observed concentration (C_{\max}).
- Area under the concentration-time curve from time 0 to infinity, calculated using the observed value of the last quantifiable concentration (AUC_{∞}).
- Area under the concentration-time curve from time 0 to the time of the last quantifiable concentration (AUC_{last}).

Exploratory Safety Endpoints

Safety will be assessed by summarizing the incidence of treatment emergent AEs (TEAEs), clinical laboratory values, physical examinations, 12-lead ECGs, and vital signs

Statistical Considerations:

Pharmacokinetics:

The PK parameters of TAK-788 and its active metabolites (AP32960 and AP32914) will be calculated based on plasma concentration - time profiles of TAK-788 and its active metabolites (AP32960 and AP32914) as described in Section 11.0, and outlined in the SAP.

A linear mixed-effects model will be used for the analysis on the natural log (ln)-transformed C_{\max} , AUC_{∞} , and AUC_{last} for TAK-788 and its active metabolites (AP32960 and AP32914). The model will include sequence, treatment, and period as a fixed-effect and subject nested within sequence as a random-effect. Each model will include calculation of least squares means (LSMs) as well as the difference between treatment LSMs.

Geometric mean ratios (GMR) and 90% confidence intervals (CI), consistent with the two one sided test [Schuirmann 1987], will be calculated using the exponentiation of the difference between treatment LSMs from the analyses on the ln-transformed C_{\max} , AUC_{∞} , and AUC_{last} (if it is needed) for TAK-788 and the combined molar C_{\max} , AUC_{∞} , and AUC_{last} (if it is needed) for TAK-788 and its active metabolites. These ratios will be expressed as a ratio of test treatment relative to the appropriate reference treatment.

Safety:

Quantitative safety data as well as the difference to baseline, when appropriate, will be summarized using the appropriate descriptive statistics.

Sample Size Justification:

The sample size calculation was based on the expected 2-sided 90% CI for the difference in the paired, log-transformed AUC_{∞} means of TAK-788 in the presence and absence of a high-fat meal. The within-patient coefficient of variation for TAK-788 C_{\max} was estimated to be 17.2% on the basis of data from a clinical study conducted in healthy subjects (TAK-788-1001). If the observed GMR for the TAK-788 AUC_{∞} in the presence and absence of high-fat is 1, with a sample size of 12, the 90% CI for the AUC_{∞} GMR is expected to be 0.881 to 1.13 on the basis of the variance assumptions. Fourteen (14) healthy adult subjects will be enrolled into this high-fat meal effect study to get at least 12 PK-evaluable subjects in each treatment arm according to the FDA guidance Assessing the Effects of Food on Drugs in INDs and NDAs – Clinical Pharmacology Considerations Guidance for Industry (FDA FE 2019).

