In the AP32788-15-101 study, following daily oral (PO) administration of TAK-788 once daily (QD), TAK-788 was readily absorbed with a median time to reach C_{max} concentration (T_{max}) of 4 hours postdose. The single-dose C_{max} and AUC_{24} of TAK-788 increased in a dose proportional manner in the dose range of 5 to 180 mg TAK-788. However, its steady state C_{max} and AUC_{24} following multiple doses increased in a less than dose proportional manner across the dose range of 5 to 180 mg. Minimal to modest TAK-788 accumulation ratios were observed at steady state (geometric mean range 1.23 to 1.52) in the dose range of 20 to 120 mg QD. At 160 mg QD, the geometric mean accumulation ratio following repeated doses was 1.06, suggesting autoinduction of the apparent oral clearance of TAK-788 likely via induction of CYP3A.

The emerging finding of autoinduction by TAK-788 at the 160 mg QD dose is consistent with the results of in vitro induction studies that have shown concentration-dependent CYP3A induction by TAK-788 and its active metabolites, suggesting a possible risk for drug-drug interactions due to induction of CYP3A and other co-regulated enzymes/transporters by TAK-788 as a potential perpetrator. The PK of the 2 active metabolites (AP32960 and AP32914) of TAK-788 were also evaluated in clinical studies. Systemic exposures to metabolites AP32960 and AP32914 in terms of molar AUC_{24} were approximately 62% (%CV: 25%) and 8% (%CV: 13%) of parent AUC_{24} respectively.

In the healthy subject study TAK-788-1001, a low-fat meal (ie, \leq 350 calories and \leq 15% calories from fat) did not affect the PK of TAK-788 in healthy subjects. At 160 mg TAK-788, 90% CIs of the GMR with a low-fat meal versus fasted conditions for C_{max} (GMR 0.964) and AUC_{∞} (GMR 0.951) fell completely within 80 -125% range.

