9.3.1 PK Measurements

9.3.1.1 Plasma PK Measurements

PK parameters from plasma concentrations of TAK-788 and its metabolites, AP32960 and AP32914, will be calculated as follows, as appropriate, following oral administration:

AUC _{last} :	The area under the concentration versus time curve, from time 0 to the last observed non-zero concentration, as calculated by the linear trapezoidal method.
AUC _∞ :	The area under the concentration versus time curve, from time 0 extrapolated to infinity. AUC _∞ is calculated as AUC _{last} plus the ratio of the last measurable blood concentration to the elimination rate constant.
AUC _{%extrap} :	Percent of AUC _∞ extrapolated, represented as (1 – AUC _{last} /AUC _∞)*100.
CL/F:	Apparent total plasma clearance after oral (extravascular) administration, calculated as Dose/AUC _∞ (TAK-788 only).
C _{max} :	Maximum observed concentration.
t _{max} :	Time to reach C _{max} . If the maximum value occurs at more than one time point, t _{max} is defined as the first time point with this value.
t _{½z} :	Apparent first-order terminal disposition phase half-life will be calculated as 0.693/λ _z .
λ _z :	Apparent first order terminal disposition phase rate constant calculated from a semilog plot of the plasma concentration versus time curve.
Vz/F:	Apparent volume of distribution during the terminal disposition phase after oral (extravascular) administration, calculated as Dose/(AUC _∞ × λ _z) (TAK-788 only).

No value for λ_z, AUC_∞, AUC_{%extrap}, CL/F, Vz/F, or t_{½z} will be reported for cases that do not exhibit a linear terminal log-linear phase in the concentration versus time profile.

No PK parameters will be calculated for subjects with detectable concentrations at 2 or fewer consecutive time points.

Individual and mean plasma concentration-curves (both linear and log-linear) will be included in the final report.

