**Table 7:1 Collection of Blood Samples for Pharmacokinetic Analysis**

Analyte	Matrix	Sampling Day	Period	Scheduled Time (hours)
mobocertinib, AP32960, and AP32914	Plasma	1	1 and 2	Predose and 0.5, 1, 2, 4, 6, 8, 12, 24, 48, 72, 120, 168, and 240 hours postdose (a) (b)

(a) If a subject experiences a serious adverse event (SAE), a blood sample for PK analysis should also be obtained at the unscheduled visit. PK samples will be collected at Early Termination at the discretion of the PI.

(b) The Period 1 Day 11 PK sample will serve as the pre-dose PK sample for Period 2.

The actual date and time of sample collection will be recorded on the source document in the CRF.

Concentrations will be listed and summarized descriptively by PK sampling time in mass units for plasma mobocertinib, AP32960, and AP32914. Summary will be done by treatment using the summary statistics listed in the CPAP. Excluded concentrations will be presented and footnoted as such in the concentration table listings, and those values will be excluded from the descriptive summary statistics. Individual subject and arithmetic mean profiles of the concentration-time data will be plotted by treatment on linear (with and without SD) and semi-log scales in mass units for each analyte. For summary statistics and arithmetic mean plots by sampling time, the nominal PK sampling time will be used, for individual subject plots by time, the actual PK sampling time will be used.

The PK parameters of mobocertinib, AP32960, and AP32914 listed in the CPAP for this study will be determined from the concentration-time profiles for subjects in the PK set using a noncompartmental analysis method in mass units. The molar  $AUC_{last}$ ,  $AUC_{\infty}$ , and  $C_{max}$  PK parameters will also be calculated for plasma mobocertinib, AP32960, and AP32914 using the molecular weights of each analyte as outlined in the CPAP. Combined molar  $AUC_{last}$ ,  $AUC_{\infty}$ , and  $C_{max}$  for plasma mobocertinib, AP32960, and AP32914 will also be presented. Actual sampling times, rather than scheduled sampling times, will be used in all computations involving sampling times. If actual sample times are missing, nominal times may be used.

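### The linear trapezoidal rule across 12 to 72 h late sampling gaps inflates the reported AUCs by a few percent and deflates CL/F and Vz/F; the fed/fasted ratio is largely protected

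*Protocol*

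**What the plan says.** - Protocol 1.0 and 5.3.1 and SAP 5.1 make AUC∞ and AUClast of TAK-788 primary endpoints. AUClast is the "Area under the concentration-time curve from time 0 to the time of the last quantifiable concentration". The same parameters for AP32960 and AP32914 are secondary.
- Protocol 9.3.1.1 gives the integration rule: AUClast runs "from time 0 to the last observed non-zero concentration, as calculated by the linear trapezoidal method". No logarithmic segment is provided for.
- The same section defines AUC∞ as AUClast "plus the ratio of the last measurable blood concentration to the elimination rate constant", CL/F as dose over AUC∞, and Vz/F as dose over AUC∞ times λz. An error in AUClast therefore passes into all three.
- SAP Table 7:1, in line with Protocol Table 3.a, samples at "Predose and 0.5, 1, 2, 4, 6, 8, 12, 24, 48, 72, 120, 168, and 240 hours postdose".
- SAP 7.10.1 says only that the analysis is noncompartmental. SAP 7.1 sends calculation details to the CPAP, which is not among the documents. SAP 7.15 records no change to the integration rule, so the protocol's rule stands on the text available.

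**The concern.** Protocol 4.1 reports a median tmax "of 4 hours postdose", so samples from 12 h on should lie in the declining phase. The gaps there are 12, 24, 24, 48, 48 and 72 h. Where concentrations fall exponentially, the linear rule overstates every such segment, always in the same direction, so the error does not average out over subjects.

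At stake are the absolute values the plan reports: geometric least-squares means and by-treatment summaries of AUC, combined molar AUC, CL/F and Vz/F. The metabolite-to-parent AUC ratios of SAP 5.4 are affected too, unless parent and metabolite profiles have similar shapes. Anyone who takes AUC or CL/F from this study for labelling, modelling or cross-study comparison inherits an error that comes from the rule and not from the drug.

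**Working it through.** **Scale: the plan's own figure.** Protocol 11.2 expects a 90% CI of 0.881 to 1.13 for the AUC∞ GMR with n = 12 and CV 17.2%. With SD = √ln(1 + 0.172²) = 0.1707, t(0.95, 10 df) = 1.812 and √(2/12) = 0.4082, exp(±1.812 × 0.1707 × 0.4082) = exp(±0.1263) = 0.881 to 1.135. The figure is reproduced. The documents give no figure for integration error.

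**Half-life (assumption).** None is stated. The only handle is the accumulation ratio R in Protocol 4.1, from once-daily patients at 20 to 120 mg. With one-compartment accumulation, t½ = 24 ln2 / [−ln(1 − 1/R)]:
- R = 1.23: 16.636/1.677 = 9.9 h
- R = 1.52: 16.636/1.073 = 15.5 h

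At 160 mg, R = 1.06 would give 5.8 h, but the protocol attributes that ratio to autoinduction, so it is not used as a single-dose half-life.

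**Bias of one segment.** For a pure exponential over a gap Δ, with x = Δ ln2/t½, linear/exact = (x/2)(1 + e^−x)/(1 − e^−x). At t½ = 12 h:
- Δ = 24 h: 0.693 × 1.25/0.75 = 1.155 (+15.5%)
- Δ = 48 h: 1.386 × 1.0625/0.9375 = 1.571 (+57%)

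**Worked profile.** One compartment, t½ = 12 h (k = 0.05776/h), ka = 0.5/h (assumed; gives tmax 4 h on this grid), C(t) = [ka/(ka − k)](e^−kt − e^−ka·t). Exact AUC∞ = 1/k = 17.312.

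| Segment | Linear | Log-down | Exact | Linear error, % of total AUC |
|---|---|---|---|---|
| 12–24 h | 5.071 | 4.880 | 4.888 | +1.06 |
| 24–48 h | 4.240 | 3.670 | 3.670 | +3.29 |
| 48–72 h | 1.060 | 0.918 | 0.918 | +0.82 |
| 72–120 h | 0.451 | 0.287 | 0.287 | +0.95 |

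Up to 12 h the linear segments sum to 7.457. With a quantification limit of 0.1% of Cmax the last sample is at 120 h. Linear AUC∞ = 7.457 + 5.071 + 4.240 + 1.060 + 0.451 + tail 0.019 = 18.298, and 18.298/17.312 = 1.057, so CL/F is 1/1.057 − 1 = −5.4%. Linear-up/log-down gives 17.220/17.312 = 0.995. With a limit of 1% of Cmax the last sample is at 72 h and the linear ratio is 1.047.

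**Ranges on the same grid, linear rule against exact AUC∞.**
- One compartment, t½ 9.9 to 15.5 h, tmax 4 to 8 h, limit 0.1 to 1% of Cmax: 1.031 to 1.059, so CL/F is −3.0% (1/1.031) to −5.6% (1/1.059). Limits from 0.01 to 2% widen the top to 1.065, at 9.9 h.
- Two compartments, R within 1.23 to 1.52 and tmax 4 h (708 settings): AUC∞ median +5.0% (5th to 95th percentile 3.5 to 6.1%), CL/F median −4.8% (−5.7 to −3.4%).
- Other one-compartment half-lives: 8 h about +6 to +7%; 20 h about +4%; 24 h about +3 to +4%; 36 h +2.6%; 48 h +1.9%.
- Linear-up/log-down: about −1.6% to 0% with one compartment, −0.5% to +1.3% with two.

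**Fed/fasted AUC∞ ratio when the true ratio is 1.**
- One compartment, slower or lagged fed absorption: linear 0.997 to 1.002, log-down 0.987 to 0.998.
- Two compartments, fasted tmax 4 h: linear 0.999 to 1.010, log-down 0.990 to 1.000. With a fasted tmax of 2 h the linear ratio reached 1.020, against 0.995 with log-down.
- Pure 3 h delay of the fed profile: linear 1.011 to 1.029, log-down 1.006 to 1.009, across the settings tried.

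**The case against.** **Only the ratio matters.** The primary objective is the meal effect, and the inference is a within-subject ratio computed with the same rule and sampling grid in both periods. This stands. A reader might infer that, because AUC is a primary endpoint, the food-effect GMR is itself wrong by 3 to 6%. The calculations do not support that: most of the error is common to both treatments, and what remains is small against a planned interval of 0.881 to 1.13. Nor is log-down uniformly closer to 1 for the ratio. It was closer under a pure delay, but slightly further away in the one-compartment profiles with slower absorption. The case for the change rests on absolute values.

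**The size is uncertain.** This stands too. Accumulation in patients on daily dosing is an indirect guide to a single dose in healthy subjects, and some induction at lower doses could make R understate the single-dose half-life. A reader might infer a fixed bias of 4% or more, but 15.5 h with a limit of 1% of Cmax gives about 3%, and longer half-lives give less. The direction is upward in every setting examined.

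**The 57% segment error looks alarming.** It belongs to a segment holding under 2% of the AUC, and adds about 0.9% to the total. The 24–48 h gap contributes most.

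**The CPAP may specify another rule.** It may. The topics that SAP 7.1 assigns to it do not name the integration rule. If it does differ, it conflicts with Protocol 9.3.1.1 and the two need aligning.

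**The rule is prespecified and reproducible.** True, and changing it affects comparability with earlier AUCs. The documents do not say which rule earlier studies used. Listing both values deals with this.

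**Conclusion.** The point holds as a cheap improvement to reported absolute exposure, not as a threat to the food-effect conclusion. On the documented sampling times, linear AUC∞ is about 3 to 6% too high, and CL/F and Vz/F low by about the same proportion, if the half-life is about 10 to 15.5 h. The AUC error is about 2 to 4% at 20 to 48 h. Linear-up/log-down on the same samples is within about 0 to 2%. The choice of rule moves the fed/fasted GMR by about 0 to 2%, most when the meal delays absorption.

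These sizes assume noise-free one- or two-compartment profiles for the parent, a half-life inferred from accumulation ratios, and quantification limits mainly of 0.1 to 1% of Cmax. The metabolites were not modelled separately; the direction is the same wherever their concentrations decline exponentially, but the size depends on their own half-lives.

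**What to change.** In Protocol 9.3.1.1, and in the CPAP if it does not already say so, replace the linear trapezoidal rule by linear-up/log-down: linear trapezoids while concentrations rise, logarithmic trapezoids, Δ(C1 − C2)/ln(C1/C2), while they fall. Apply it to TAK-788, AP32960 and AP32914 in both periods. List the linear-rule AUCs as a sensitivity value. Record the change in SAP 7.15, and decide whether it counts as a major change to a primary endpoint's definition, which Protocol 11.1 says is to be reflected in an amendment.

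The cost is one wording change and one setting in the PK software, with no new samples, subjects or visits. The downside is that absolute AUCs come out a few percent lower and cannot be compared directly with any earlier linear-rule values unless both are listed.
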